2 STATISTICAL HYPOTHESES

The study will estimate the true population proportion of self-administration-related endpoints for ZLP-AI. No formal statistical hypothesis testing will be done.

2.1 Multiplicity adjustment

No multiplicity adjustment will be performed.

3 ANALYSIS SETS

- Screened Set (ScS): all participants who have signed the informed consent form (ICF).
- Enrolled Set (ES): all participants who have signed the informed consent form and are eligible candidates for the study (screen failures excluded).
- Safety Set (SS): all participants in ES who received at least 1 dose of ZLP with the ZLP-AI combination product.
- Pharmacokinetic per-Protocol Set (PK-PPS): all participants in SS who have at least 1 quantifiable PK measurement during the study without important protocol deviations that would affect the PK.

4 STATISTICAL ANALYSIS

4.1 General considerations

Statistical analysis and generation of tables, figures, participant data listings, and statistical output will be performed using SAS® Version 9.4 or higher. If a different SAS version or different software will be used during the statistical analysis, then this should be reported in the CSR. All tables and listings will use Courier New font size 9.

All study data will be presented in participant data listings. Descriptive statistics will be displayed to provide an overview of the study results. For continuous variables, descriptive statistics will include number of participants with available measurements (n), mean, standard deviation (SD), median, minimum, and maximum. For categorical variables, the number and percentage of participants in each category will be presented. Unless otherwise noted, the denominator for percentages will be based on the number of participants included in the respective analysis set.

Participants with missing data can generally be accounted for using the following approaches:

- For summaries of demographics and Baseline characteristics: summarize percentages based on all participants in the analysis set and include a “Missing” category (corresponding to participants with missing data for the variable being summarized) as the last row in the list of categories being summarized.
- For summaries of safety or other variables, unless otherwise specified: summarize percentages based only on those participants with observed data for the variable being summarized. As the denominator may be different from the number of participants in the analysis set being considered, the denominator should be displayed in the table. The general format for displaying this will be “n/Nsub (%)”.

Unless otherwise noted, all percentages will be displayed to one decimal place. No percentage will be displayed for zero counts, and no decimal will be presented when the percentage is 100%.

For the purpose of the tabulations the lower and upper confidence limits for the percentages will be truncated at 0 and 100% respectively.

For PK concentrations, summary statistics will include geometric mean, geometric coefficient of variation (CV), 95% confidence intervals (CIs) for geometric mean, arithmetic mean, SD, median, minimum, and maximum. All summaries of PK variables will be based on the observed values. No imputation will be used.

Decimal places for descriptive statistics will always apply the following rules:

- “n” will be an integer;
- Mean, SD, and median will use one additional decimal place compared to the original data;
- CV [%] will be presented with one decimal place;
- Minimum and maximum will have the same number of decimal places as the original value.

Derived variables in general will display the mean, SD and median to 1 more decimal place than the variables used in the derivation. If the number of decimal places reported in the raw data is varied, then use either the maximum raw number of reported decimal places or 3, whichever is the lowest, as a guide for the descriptive statistics.

If any statistical testing is to be performed then this will be presented as p-values rounded to four decimal places. P-value less than 0.001 will be presented as “<0.0001” and p-value greater than 0.9999 will be presented as “>0.9999.” Statistical comparison will be two-sided and will be performed at the 0.05 level of significance.

If no participants have data at a given time point, for example, then only n=0 will be presented. However, if n<3, present the n, minimum and maximum only. If n=3, n, mean, median, minimum and maximum will be presented only. The other descriptive statistics will be left blank.

All study data but PK will be summarized in the Safety population. PK will be summarized in the PK-PPS.

Once the last study participant has completed the SFU, or the last study participant has prematurely discontinued prior to reaching the SFU, the database will be locked and TFLs will be produced.

4.1.1 Analysis time points

Summaries by study visits will be performed at the nominal visits and no mapping to analysis visits windows will be performed, except for early termination visit as specified in Section 4.1.3. Unscheduled visits (if any) will only be listed and will not be remapped. An individual participant listing indicating the actual visit dates will be created in SS.

4.1.1.1 Relative day for listings

Relative day will be provided in different listings and will be calculated as follows from the first dose of IMP:

- If the start (stop) date occurred on or after the first dose, but prior to the drug stop date, relative day is calculated as start (stop) date minus first dose date + 1 (the day of first dose will be Day 1).
- If the start (stop) date occurred before the first dose, the relative day is calculated as date of first dose of ZIP-AI minus the start (stop) date (the day prior to first dose will be Day - 1).
- If the start (stop) date occurred after the last dose of ZIP-AI, the relative day to the most recent dose is calculated as start (stop) date minus last dose of ZIP-AI including a '+' to denote post treatment days (e.g. the day after last dose will be Day +1).

If start/stop date is missing or partially missing then relative date will be calculated based on imputed dates, see Section 4.1.1.4.

Of note, since Screening visit is performed on the same date with dosing (Visit 1, Day 1) it is expected that the relative date of Screening visit will be the same as the relative date of Visit 1; this is relative day=1.

4.1.1.2 Missing data

Missing data for any of the study endpoints or any other data will not be imputed (except for missing date and times, see Section 4.1.1.4); observed cases will only be used in the summary.

4.1.1.3 Handling of repeated and unscheduled measurements

All repeated and/or unscheduled measurements will be presented in the listings, where applicable. The following general rules will apply to all repeated and unscheduled measurements:

- For repeated or unscheduled measurements obtained prior to the first self-injection with ZLP-AI the latest reliable value (scheduled or unscheduled) will be used in the calculation of descriptive statistics (i.e., Screening and/or Baseline) as defined in Section 4.1.2.
- For repeated or unscheduled measurements obtained at Day 1 and prior to first self-injection with ZLP-AI, the latest reliable value (scheduled or unscheduled) will be defined as the Baseline.
- For repeated or unscheduled measurements obtained at any time point after first self-injection with ZLP-AI, the original values (if non-missing) will be used in the calculation of changes from Baseline and for the descriptive statistics (i.e., in summaries by time point).

4.1.1.4 Handling of missing dates and times

Partially or completely missing dates may be imputed for the following reasons:

- Classification of Adverse Events (AEs) as Treatment Emergent AEs;
- Classification of medications as past, prior, baseline or concomitant medications;
- Duration of AEs

Imputed dates will not be shown in listings. All dates will be displayed as reported in the database.

The following rules will be applied for partially or completely missing start dates:

- If year, month and day are all missing then assign the date of first dose of ZLP-AI. If an imputed start date is after the specified end date, then assign January 01 of the year of the end date, or the date of screening if this is later (if the latter imputation results in an end date that is earlier than the start date, then use January 01).
- If month and day are missing, and year is:
 - the same as the year of the first dose of ZLP-AI then assign the month-day of first dose of ZLP-AI. If the imputed start date is after the specified end date, then assign January 01, or the month-day of screening date if this is later (if the latter imputation results in an end date that is earlier than the start date, then assign January 01);
 - not the same as the year of the first dose of ZLP-AI then assign January 01.
- If only day is missing, and month-year is:
 - the same as the month-year of the first dose of ZLP-AI then assign the day of first dose of ZLP-AI. If the imputed start date is after the specified end date, then assign first day of the month, or the day of screening date if this is later (if the latter imputation results in an end date that is earlier than the start date, then assign first day of the month);
 - not the same as the month-year of the first dose of ZLP-AI then assign the first day of the month.

Of note, as per CRF design only start date of Previous Zilucoplan Use Prior to Study Entry is collected. Therefore, End date will be imputed with Start date in order to derive these as past medications.

The following rules will be applied for partial stop dates:

- If only the month and year are specified, then use the last day of the month;
- If only the year is specified, then use December 31 of the known year or discharge date if this is earlier than December 31st of that year;
- If the stop date is completely unknown, then use discharge date or data cut-off date.

Note: Discharge date refers to the date of the end of study visit for completed participants or for participants that were withdrawn. For any AEs with known start date after the date of discontinuation, the date of last contact will be used as the discharge date. For participants still ongoing in the study at the time of the data cut-off, and for whom no discharge date is available, the date of the data cut-off will be used instead of the discharge date.

In the event of ambiguity or incomplete data which makes it impossible to determine whether a medication/AE was concomitant/treatment emergent or not, the medications/AEs will be considered as concomitant/treatment emergent. Any medication with a start date on the first date of dose, will be assumed to be concomitant.

Imputed AE dates will be used for the calculation of duration of AEs, defined as:

Duration of AE = stop date – start date + 1.

4.1.1.5 Analysis periods

Based on the specific requirements of the analyses, the concept of the definition of periods need to be considered for the study, is defined in detail below.

The total duration of study participation for all participants will be up to approximately 21 days, including single Screening/Day 1 Visit, a 14-days Intervention Period and a safety follow up period of up to 7 days (± 3). The end of the study is defined as the date of the last visit of the last participant in the study.

Screening Period: starts at the day of ICF signature (any time prior to the first dosing with ZLP-AI on site) and ends at the date/time of first application of ZLP-AI on site.

Intervention Period (Treatment Period): starts at the date/time of the first application of ZLP-AI on site. The end of intervention period is the date of the last ZLP-AI application on site or the date of Early Withdrawal Visit was performed, as applicable.

All participants in the Safety Set will be considered to have entered the Intervention Period. A participant is considered to have completed the Intervention Period if the Visit 8 visit on site at day 14 has been performed.

If a participant does not have the last planned visit or Early Withdrawal visit, then either the date of the last scheduled (on site or phone call visits) or unscheduled visit during the considered period or the date of the last known dose of study drug during the considered period, whichever is later, will define the end date of the Intervention Period.

Safety Follow-Up Period: one day after the end of the Intervention Period ending after the final assessments on the Safety Follow-up visit. Participants with assessment after the Intervention Period are considered to have started the Follow-up Period.

The end of study for each participant is defined as the last visit attended (as planned, Early Withdrawal, phone visit) in the Intervention Period or in the safety follow up period. If a participant does not have the last planned visit or Early Withdrawal visit, then either the date of the last scheduled (on site or phone call visits) or unscheduled visit during the considered period or the date of the last self-injection with ZLP-AI intake during the considered period, whichever is later, will define the end date of the Intervention Period.

A participant is considered to have completed the study if he/she has completed all periods of the study, including the Intervention Period and SFU phone call.

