**Table 1-1: Schedule of study assessments**

Period	Screening Period	Treatment Period								EW b (In-clinic)	SFU Visit c (Phone call)
Name	Screening (In-clinic)	Day 1 (In-clinic)	Day 2 (Phone call) a	Day 4 (Phone call) a	Day 6 (Phone call) a	Day 8 (Phone call) a	Day 10 (Phone call) a	Day 12 (Phone call) a	Day 14 (In-clinic)		
Visit #	1		2	3	4	5	6	7	8	9	
Day	1		2	4	6	8	10	12	14	(Final dose +7±3 days)	
Participant completes postinjection SIAQ (SIAQ POST module) j		X							X		
Study personnel collect ZLP-AI devices from each participant to send to UCB for structural/mechanical integrity assessment t m		X							X		
Drug and device accountability									X		
Record TEAEs, SAEs, ADEs, SAEs, medication errors, ISR, and device deficiencies n		X	X	X	X	X	X	X	X	X	
Blood sampling for ZLP plasma concentrations o	CCI										

ADE=adverse device effect; AE=adverse event; AI=auto-injector; βHCG=beta human chorionic gonadotropin; C-SSRS=Columbia-Suicide Severity Rating Scale; EW=early withdrawal; IMP=investigational medicinal product; ISR=injection site reaction; IXRS=interactive response technology;

MGFA=Myasthenia Gravis Foundation of America; PK=pharmacokinetic; SAE=serious adverse device event; SAE=serious adverse event; SFU=Safety

Follow-Up; SIAQ=Self-Injection Assessment Questionnaire; ZLP=zilucoplan

a Telephone visits which would be scheduled to occur on a weekend day may be skipped, and the data for the respective days (Saturday and Sunday) will be collected on the next clinic business day (Monday).

b If a study participant permanently withdraws from the study, the study participant should return to the clinic for an EW Visit as soon as possible but no later than the next scheduled in-clinic visit.

c Study participant will be required to perform a SFU telephone call 7 days (±3 days) after their final study dose of ZLP using the ZLP-AI.

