## **7 DISCONTINUATION OF STUDY MEDICATION AND PARTICIPANT DISCONTINUATION/WITHDRAWAL**

### **7.1 Discontinuation of study medication**

Dosing of a study participant must be immediately and permanently discontinued if:

- Study participant is diagnosed with meningococcal disease
- In the opinion of the Investigator and/or Sponsor, it is unsafe for the study participant to continue dosing with study medication (eg, suspected pancreatitis)

In circumstances where permanent discontinuation from study medication may occur, the Investigator is to discuss with the study participant the appropriate processes for discontinuation from study medication and must discuss with the study participant the options for continuation of the assessments in the SoA (Section 4.3), including different options of follow up (eg, in person, by phone/mail, in correspondence/communication with other treating physicians, from the review of medical records) and collection of data, including endpoints and AEs. Study participants who discontinue study medication should not be automatically removed from the study. Whenever safe and feasible, it is imperative that study participants remain on the study to ensure safety surveillance and/or collection of outcome data. The Investigator must document the level of follow up that is agreed to by the study participant, any changes to the scheduled visits and assessments, and the plan for follow up that is agreed to by the participant. In regard to changes to scheduled visits, for the level of follow up, it is recommended that the Early Withdrawal Visit and the SFU Visit be prioritized. If the study participant does not want to continue the study medication and withdraws consent (Section 7.2), the Investigator should contact the Medical Monitor, whenever possible, to discuss the withdrawal of a participant in advance.

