4.2.2 Main analytical approach

The proportion (p) of effective self-administrations overall will be summarized based on the number of ZLP-AIs used and returned, within participants in the Safety Set (SS):

$$P = [\text{Number of all ZLP-AIs with complete dose delivery}] / [\text{Number of all ZLP-AIs used and returned}]$$

The denominator of the fraction should include all ZLP-AIs that were used (self-administered) during the Intervention Period and returned, as captured in the drug accountability log. Of note, since it is possible that complete dose delivery may be observed within malfunctioned ZLP-AIs the denominator should also include the malfunctioned auto injectors (if any).

The 95% CI of the proportion based on the Exact Binomial method will be reported as well.

Based on the above calculation no missing data are expected to be observed.

In order to provide further insight into the evaluation of the primary estimand, the following will also be summarized:

- Number of injections performed by (study participant, site personnel, caregiver).

- Number of injections dispensed

- Number of injections returned, used and malfunctioned

- Number of injections returned used and not malfunctioned

- Number of injections returned, unused

- Reason for Discrepancy between dispensed and returned injections (lost, stolen, missing, other).

A by participant individual data listing will be created reporting detailed information on the ZLP-AIs kits administered and returned in clinic.

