4.5.3 Tolerability - Injection Site Reactions and Medication Errors

Injection Site Reactions

An AE reported in the eCRF with a start date/time on or following to the first self-administration of ZLP AI through the final self-injection and until the safety follow up which is coded into MedDRA High Level Terms of “Administration site reactions NEC” or “Injection site reactions” will be evaluated as Injection Site Reaction (ISR). ISRs will be summarized in SS overall, by intensity and by seriousness. Summaries will be based on the number and percentage of participants who experienced at least one ISR event by MedDRA SOC, HLT and PT followed by the number or ISR events.

A separate assessment of tolerability at injection site (as part of physical examination and as defined in the study protocol) is performed during the on- site visits assessing pain, burning, erythema, itching, swelling and bruising based on a Likert type scale of 0 to 3. Greater grade indicates more severe injection site reaction. For each of the assessments a shift table will be created to show the shift of injection site reaction grading from Visit 1 to Visit 8.

ISR and tolerability data will be listed in SS.

Medication Errors

An adverse reaction is a response to a medicinal product which is noxious and unintended (Directive 2001/83/EC, Article 1 (11)). An adverse event which is reported as a consequence of a medication error is considered as an adverse reaction.

Participants with medication errors associated with adverse reactions will be identified via the eCRF- Adverse Event form as reported by the investigator. The number and proportion of participants experiencing such AEs during the Intervention Period will be summarized by MedDRA SOC, HLT and PT in SS. A by-participant listing in SS will also be created listing all the AEs associated with medications errors reported in the study.

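### SAP 4.1.1.5 ends the Intervention Period on Day 1 for a participant who attends Visit 8 without injecting there, in conflict with the rest of the SAP

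*SAP*

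**What the plan says.** SAP 4.1.1.5 says that the Intervention Period "starts at the date/time of the first application of ZLP-AI on site", and then: "The end of intervention period is the date of the last ZLP-AI application on site or the date of Early Withdrawal Visit". The follow-up period begins the next day. A fallback covers some participants: "If a participant does not have the last planned visit or Early Withdrawal visit, then either the date of the last scheduled" or unscheduled visit or the last known dose is used, whichever is later. The same section describes a 14-day Intervention Period and treats it as completed once Visit 8 has been performed, with no requirement that an injection took place there.

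Two analyses depend on the period by name:

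- Primary proportion, SAP 4.2.2: "The denominator of the fraction should include all ZLP-AIs that were used (self-administered) during the Intervention Period and returned".
- Medication errors associated with adverse reactions, SAP 4.5.3: "The number and proportion of participants experiencing such AEs during the Intervention Period will be summarized".

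Protocol 7.1 allows a participant to stop the device and stay in the study: "Study participants who discontinue study medication should not be automatically removed from the study". Footnote b of the protocol's schedule ties the EW visit to leaving the study: "If a study participant permanently withdraws from the study, the study participant should return to the clinic for an EW Visit".

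**The concern.** Each participant has 14 planned applications. The Day 1 and Day 14 applications are in the clinic and the other 12 are at home. An end date that looks only at clinic applications therefore depends on whether an injection was given at Visit 8. If the participant came to Visit 8 but had already dosed at home that day, or missed that dose, the last clinic application is the one on Day 1. The fallback would use the last dose at any location, but it is meant for people with neither Visit 8 nor an EW visit, so it does not apply.

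The period is then one day long, and the home injections fall in what the SAP calls follow-up. Because 4.2.2 and 4.5.3 both refer to the Intervention Period, the primary denominator and the medication-error table would depend on how a programmer resolves the conflict, possibly after the data have been seen.

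**Working it through.** **Inputs.** 14 self-administrations per participant, with clinic visits on Days 1 and 14 (SAP 1.2; protocol Table 1-1). At least 25 participants and about 350 self-administrations (SAP 5). The documents do not say how many participants might attend Visit 8 without injecting; call this k, an assumption.

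**The plan's own figure.** 25 × 14 = 350, as stated.

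**Who is affected.**

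- Injects at Visit 8: the period ends on Day 14. Not affected.
- Has an EW visit: the period ends at that visit. Home devices stay in.
- Has neither Visit 8 nor an EW visit: the fallback applies. Home devices stay in.
- Attends Visit 8, no injection there, no EW visit: the last clinic application is Day 1, so the length is 1 − 1 + 1 = 1 day.

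**Devices for one affected participant.**

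- Day 14 dose taken at home: 14 used, 1 inside the literal period, 13 outside. Span in 4.2.3: 14 − 1 + 1 = 14.
- Last dose on Day 13: 13 used, 1 inside, 12 outside. Span in 4.2.3: 13 − 1 + 1 = 13.

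**Study level.** The literal denominator is 14(25 − k) + k = 350 − 13k. The full denominator is 350 (Day 14 dose at home) or 350 − k (last dose Day 13).

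| k (assumed) | Literal | Full | Share dropped |
|---|---|---|---|
| 1 | 337 | 350 or 349 | 3.7% or 3.4% |
| 2 | 324 | 350 or 348 | 7.4% or 6.9% |
| 3 | 311 | 350 or 347 | 11.1% or 10.4% |
| 5 | 285 | 350 or 345 | 18.6% or 17.4% |

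**Numerator.** The 4.2.2 formula counts every device with complete delivery and sets no period limit. If all deliveries are complete and k = 1, the literal result is 350/337 = 103.9% (or 349/337 = 103.6%). No exact binomial interval exists for such a count, so the literal reading cannot be programmed as it stands.

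**If a programmer trims both terms (k = 1, exact 95% CI).**

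- No failures: the lower limit moves from 98.95% (350/350) to 98.91% (337/337). With k = 5 it is 98.71% (285/285).
- Five failures (assumed), full denominator: 345/350 = 98.57% (96.70 to 99.53).
- The same five, all among retained devices: 332/337 = 98.52% (96.57 to 99.52).
- The same five, all among the affected participant's dropped home devices: 337/337 = 100% (98.91 to 100).

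The estimate barely moves unless failures cluster in the affected participants.

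**Medication errors.** SAP 4.5.3 counts events during the Intervention Period. With a one-day period, events on Days 2 to 14 for that participant are outside it.

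**The case against.** The strongest reply is that the intent is clear from elsewhere. The lead sentence and displayed formula in 4.2.2 count every used and returned device in the Safety Set. The estimand runs from Visit 1 to Visit 8. SAP 4.1.1.5 itself gives 14 days and a completion rule based on attendance, and 4.2.3 uses first and last dose dates wherever the dose was given. A sensible programmer would keep the home devices. This stands as evidence of intent, but it also shows that the end-date sentence disagrees with its surroundings.

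The case is also narrow. When the device is stopped early, SAP 4.1.3 expects an EW visit and protocol 7.1 recommends giving that visit priority. A pregnancy leads to withdrawal and an early discontinuation visit (protocol 7.2 and 8.3.5). Either visit ends the period and keeps the home devices. What mainly remains is a Day 14 dose taken at home or missed before an attended Visit 8, plus early stoppers for whom the recommended EW visit does not happen.

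A reader might infer more than the documents support:

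- *That home devices are definitely excluded, turning real failures into a 100% result.* This requires trimming a numerator that carries no period limit, and reading one sentence against several others.
- *That exposure is distorted.* SAP 4.5.1 calculates it from dose dates.
- *That TEAE counts change.* SAP 4.5.2.1 defines TEAEs from injection dates and last contact.
- *That a late EW visit brings syringe-period medication errors into the table.* The schedule notes restrict recording of medication errors to the days of auto-injector use. SAP 4.5.2 leaves events after the return to MG0011 or commercial supply out of this study unless clearly tied to the device.

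**Conclusion.** The end-date rule is wrong for one reachable case: Visit 8 attended, no injection there, no EW visit. It gives a one-day period and contradicts the 14-day description, the completion rule, the estimand, the 4.2.2 formula and the 4.2.3 span.

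The literal consequence is up to 13 home devices per affected participant leaving the denominator (3.7% of 350), a proportion that can exceed 100%, and the loss of that participant's Day 2 to Day 14 events from the medication-error summary. The percentages assume 25 participants with 14 planned devices each. The frequency of the case is unknown.

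This is an inconsistency to repair rather than evidence that the primary result will be biased. The effect on the estimate is small unless failures concentrate in the affected participants.

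**What to change.** In SAP 4.1.1.5, remove the *on site* condition from the end-date rule and define the end as follows:

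*The Intervention Period ends on the latest of (a) the last ZLP-AI application at any location, (b) the Visit 8 date, if attended, and (c) the Early Withdrawal Visit date, if performed.*

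Keep the fallback for participants with neither visit. This wording agrees with the completion rule, with the fallback, and with the C-SSRS summaries in 4.5.5.4, which place Visit 8 and the EW visit within the Intervention Period. Ending the period at the last dose alone and dropping the EW anchor would not work. A participant last dosed on Day 13 would then attend Visit 8 in follow-up, and EW assessments would also fall outside the period.

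In SAP 4.2.2, state that numerator and denominator both cover all ZLP-AIs used in that period, in the clinic or at home, and returned.

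The cost is two short edits to the SAP, with no new data and no protocol change.
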